5.1.3 Subject Exclusion Criteria

The subject must be excluded from participating in the trial if the subject:

All Subjects:

1. Is currently participating and receiving trial therapy or has participated in a trial of an investigational agent and received trial therapy or used an investigational device within 28 days before trial Day 1.
2. Treatment with a cytochrome P450 3A4 (CYP3A4) strong inhibitor or inducer within 7 days prior to enrollment. See Section 12.6 for information about strong inhibitors/inducers of CYP3A4.
3. Treatment with anticancer therapy or thoracic radiation therapy within 14 days before the first dose of treatment.

Exception: Subjects with CLL may receive ibrutinib (or similar for CLL) up to 7 days before trial Day 1.

4. Has known clinically active central nervous system involvement.
5. Has a known history of immunosuppression or is receiving systemic steroid therapy or any other form of systemic immunosuppressive therapy within 7 days prior to the first dose of trial treatment.
 - The use of physiologic doses of corticosteroids may be approved after consultation with the Sponsor.
6. Has had a prior anticancer monoclonal antibody within 4 weeks prior to trial Day 1 or who has not recovered (ie, \leq Grade 1 or at baseline) from AEs due to agents administered more than 4 weeks earlier.
7. Grade 2 or higher nonhematological toxicities from prior therapy. Residual toxicity of Grade 1 from prior therapy or persistent treatment-related Grade 1 neurotoxicity will be allowed.

Note: If subject received major surgery, they must have recovered adequately from the toxicity and/or complications from the intervention prior to starting therapy.

Note: Toxicity that has not recovered to \leq Grade 1 is allowed if it meets the inclusion requirements for laboratory parameters defined for each tumor type.

8. Has undergone prior allogeneic hematopoietic stem cell transplantation within the last 5 years. (Subjects who have had a transplant greater than 5 years ago are eligible as long as there are no symptoms of Graft versus Host Disease.)
9. Has a known additional malignancy that is progressing or requires active treatment. Exceptions include basal cell carcinoma of the skin, squamous cell carcinoma of the skin, or in situ cervical cancer that has undergone potentially curative therapy.
10. Has active autoimmune disease that has required systemic treatment in past 2 years (ie, with use of disease modifying agents, corticosteroids or immunosuppressive drugs). Replacement therapy (eg, thyroxine, insulin, or physiologic corticosteroid replacement

therapy for adrenal or pituitary insufficiency, etc.) is not considered a form of systemic treatment and is allowed.

11. Has a history of (non-infectious) pneumonitis that required steroids or current pneumonitis.
12. Has an active infection requiring intravenous systemic therapy.
13. Has known psychiatric or substance abuse disorders that would interfere with cooperation with the requirements of the trial.
14. Is pregnant or breastfeeding, or expecting to conceive or father children within the projected duration of the trial, starting with the pre-screening or screening visit through 120 days after the last dose of trial treatment.
15. Has received prior therapy with an anti-PD-1, anti-PD-L1, anti-PD-L2 anti-CD137, or anti-CTLA-4 antibody (including ipilimumab or any other antibody or drug specifically targeting T-cell co-stimulation or checkpoint pathways) or CAR-T cell therapy or with an agent directed to another stimulatory or co-inhibitory T-cell receptor.
16. Previously treated with a CDK inhibitor (eg, dinaciclib or flavopiridol).
17. Has a known history of human immunodeficiency virus (HIV) infection. No HIV testing is required unless mandated by local health authority.
18. Has a known history of or is positive for hepatitis B (hepatitis B surface antigen [HBsAg] reactive) or hepatitis C (hepatitis C virus [HCV] RNA [qualitative] is detected).
19. Has received a live vaccine within 30 days prior to first dose.
20. Has known current symptomatic congestive heart failure, unstable angina pectoris, or cardiac arrhythmia.

CLL

21. Subject with Richter's Transformation.

MM

22. Subjects with non-secretory or oligo-secretory myeloma, plasma cell leukemia, or Waldenström's macroglobulinemia.
23. History of primary amyloidosis, hyperviscosity or POEMS syndrome (plasma cell dyscrasia with polyneuropathy, organomegaly, endocrinopathy, monoclonal protein, and skin changes).

DLBCL

24. Subjects with primary mediastinal B-cell lymphoma.
25. Subject with Richter's Transformation.

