5.1.2 Subject Inclusion Criteria

In order to be eligible for participation in this trial, the subject must:

All Subjects:

1. Be willing and able to provide written informed consent/assent for the trial. The subject may also provide consent/assent for Future Biomedical Research. However, the subject may participate in the main trial without participating in Future Biomedical Research.
2. Be \geq 18 years of age on day of signing informed consent.
3. Female subjects of childbearing potential should have a negative urine or serum pregnancy within 72 hours prior to receiving the first dose of trial medication. If the urine test is positive or cannot be confirmed as negative, a serum pregnancy test will be required.

4. Female subjects of childbearing potential must be willing to use an adequate method of contraception as outlined in Section 5.7.2 - Contraception, for the course of the trial through 120 days after the last dose of trial medication.

Note: Abstinence is acceptable if this is the usual lifestyle and preferred contraception for the subject.

5. Male subjects of childbearing potential must agree to use an adequate method of contraception as outlined in Section 5.7.2 - Contraception, starting with the first dose of trial therapy through 120 days after the last dose of trial therapy.

Note: Abstinence is acceptable if this is the usual lifestyle and preferred contraception for the subject.

6. Must have a performance status of 0 or 1 on the Eastern Cooperative Oncology Group (ECOG) Performance Scale.
7. Cardiac function suitable for hydration guidelines outlined in [Table 6](#) and [Table 7](#) per investigator and/or cardiologist.
8. Be able to provide newly obtained (within 3 months) bone marrow biopsy material for biomarker analysis. If bone marrow biopsy was performed within 3 months before screening but subject had anticancer treatment after biopsy, the bone marrow biopsy and aspiration should be repeated.

9. Must demonstrate adequate organ function as defined below (Table 1):

Table 1 Subject Inclusion Criteria - Adequate Organ Function

System	Laboratory Value
Hematological	
ANC	> 1,500/ μ L (unless due to marrow involvement)
Platelets ^a	\geq 100,000/ μ L (\geq 30,000/ μ L for CLL)
Hemoglobin ^a	\geq 8.0 g/dL or \geq 1.24 mmol/L ^a
Renal	
Creatinine OR	\leq 1.5 X ULN OR

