5.5.2 Prohibited Concomitant Medications and Therapies

The medications, supplement, and other substances prohibited prior to Screening are listed in Section 5.1.3 with the subject exclusion criteria.

Dinaciclib:

Dinaciclib is metabolized by the human hepatic enzyme CYP3A4. In vitro metabolism studies indicated that dinaciclib is a competitive inhibitor of CYP1A2, as well as an irreversible metabolism-dependent inhibitor of CYP3A4/5. Coadministration of dinaciclib with strong CYP3A4/5 inhibitors may increase the concentration of dinaciclib, and coadministration of dinaciclib with strong CYP3A4/5 inducers may decrease the concentration of dinaciclib.

Since dinaciclib is a substrate of CYP3A4, concomitant use of other drugs that are strong inhibitors or inducers of CYP3A4 is prohibited while the subject is enrolled in this trial except for required steroid premedication. See Section 12.6 for information about strong inhibitors/inducers of CYP3A4.

If the use of a medication that is a strong CYP3A4 inhibitor or inducer is medically necessary and an alternate therapeutic agent that is not a strong inhibitor or inducer of CYP3A4 is not available, then the subject must discontinue treatment with dinaciclib.

The investigator should be alerted if the subject is taking any agent known to affect or with the potential to affect selected CYP450 isoenzymes.

Additional information regarding drug interactions with cytochrome P450 isoenzymes can be found at the following website: <http://medicine.iupui.edu/clinpharm/ddis/>.

Pembrolizumab and dinaciclib: Subjects are prohibited from receiving the following therapies during the Screening and Treatment phase of this trial:

- Antineoplastic systemic chemotherapy, biological therapy, or immunotherapy
- G-CSF for primary prophylaxis during Cycle 1 in Dose Evaluation
- Granulate-macrophage colony-stimulating factor (GM-CSF)
- Investigational agents other than pembrolizumab and dinaciclib
- Radiation therapy
 - Note: Radiation therapy to a symptomatic soft tissue lesion, bone lesions, or to the brain may be allowed after consultation with Sponsor.
 - Thoracic radiation therapy is not allowed within 14 days before the first dose of treatment.

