7.1.2.8 Assessment of Disease and Tumor Response

7.1.2.8.1 CLL Response Assessments

Disease assessments or scans performed as part of routine clinical management are acceptable for use as the screening scan if they are of diagnostic quality and performed within 28 days prior to Cycle 1 Day 1.

CT scans of the neck, chest, abdomen, and pelvis will be obtained at screening within 28 days of Cycle 1 Day 1. Follow-up CT scans of the neck should be performed if enlarged lymph nodes (defined as ≥ 1.5 cm) are detected on the screening CT neck scan or if medically indicated by the discretion of the treating physician.

CT scans will be repeated every 3 cycles (approximately 9 weeks) despite any delays in treatment. CT scans will be read locally.

Response will be determined locally according to the iwCLL criteria, using results of the subject's CT scan, hematology laboratory results (complete blood counts), and presence of CLL symptoms as described in Section 12.7. Response assessments should be completed in conjunction with the subject's CT scan schedule.

If medically appropriate, a confirmatory assessment of the initial progression event should be performed within 9 weeks. A CT scan of the neck (if indicated), chest, abdomen and pelvis and hematology laboratory (complete blood counts) will be obtained, and the presence of CLL symptoms will be determined at each response assessment time point.

7.1.2.8.2 Multiple Myeloma Response Assessments:

7.1.2.8.2.1 Myeloma Laboratory Testing Disease Measurements

Baseline

For subjects with MM, collect serum and urine samples within 28 days of Cycle 1 Day 1 for baseline disease assessment. Baseline serum and urine (24 hr) M protein levels will be assessed by electrophoresis and immunofixation. Free light chain (FLC) levels and ratio will also be assessed.

Serum electrophoresis (SPEP)

If serum M protein by electrophoresis (SPEP) ≥ 1 g/dL at baseline, SPEP will be assessed after each cycle.

Urine electrophoresis (UPEP)

If urine M protein (24 hr) by electrophoresis (UPEP) ≥ 200 mg, UPEP (24 hr) will be assessed after each cycle.

FLC

For subjects with non-secretory myeloma (SPEP < 1 g/dL and UPEP < 200 mg/24 hr) at baseline, but serum light chain ≥ 10 mg/dl, serum FLC will be assessed after each cycle.

Best Response

Laboratory assessments should be repeated to confirm best response, including SPEP and UPEP, serum and urine immunofixation, and FLC. Bone marrow biopsy is recommended to confirm CR.

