7.1.2.8.3 DLBCL Disease Response Assessment

Disease assessments or scans performed as part of routine clinical management are acceptable for use as the screening scan if they are of diagnostic quality and performed within 28 days prior to Cycle 1 Day 1. CT and PET should be used throughout the trial. For lymphomas that are not PET-avid at screening, PET does not need to be repeated in follow-up assessments.

The site trial team must review pre-trial images to confirm the subject has measurable disease as defined in the inclusion criteria.

PET/CT scans of the chest, abdomen, and pelvis will be repeated every 3 cycles (9 weeks) or when medically indicated despite any delays in treatment.

PET/CT scans of the neck should be performed if enlarged lymph nodes are detected during the PE exam or if otherwise medically indicated by the discretion of the treating physician.

PET/CT scans will be read locally.

Response assessment by CT or PET/CT is based on the Revised Response Criteria for Malignant Lymphoma [3] described in Section 12.9. If complete remission is documented by both CT and FDG-PET, subsequent assessments may be by CT only, with PET used only if relapse or recurrence is suspected. Local reading (investigator assessment with site radiology reading) will be used to determine subject eligibility and for subject management.

Assessment of lymphoma B symptoms should occur with each lymphoma disease response assessment (Section 12.10). If a subject has radiographically progressive disease but is clinically stable and suspicious for pseudo-progression, the subject can continue trial treatment after consultation with the Sponsor. Additionally, the subject should be rescanned within 4 to 6 weeks for confirmation. The subject should discontinue trial treatment if they meet discontinuation criteria described in Sections 5.8.1, 7.1.2.7.2, and 7.1.2.7.3.

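### The response baseline may be 28 days old while some prior anticancer therapy may continue to 14 days (ibrutinib or similar in CLL: 7 days) before first dose, so shrinkage from the earlier drug can count toward a PR

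*Combined protocol and SAP*

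**What the plan says.** **Washout (Section 5.1.3).** Exclusion 3 bars "Treatment with anticancer therapy or thoracic radiation therapy within 14 days before the first dose of treatment". Its exception reads "Subjects with CLL may receive ibrutinib (or similar for CLL) up to 7 days before trial Day 1". Two classes have longer limits. Exclusion 6 covers a subject who "Has had a prior anticancer monoclonal antibody within 4 weeks prior to trial Day 1", and exclusion 1 covers one who "received trial therapy or used an investigational device within 28 days before trial Day 1".

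**Baseline age.** For DLBCL (7.1.2.8.3), routine scans are "acceptable for use as the screening scan if they are of diagnostic quality and performed within 28 days prior to Cycle 1 Day 1". Section 7.1.2.8.1 has the same rule for CLL. For MM (7.1.2.8.2.1), sites "collect serum and urine samples within 28 days of Cycle 1 Day 1 for baseline disease assessment". Section 7.1.5.1 and flow chart note c accept results from before consent if they fall within the window.

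**Repeat rule.** The only rule to repeat a test after intervening therapy concerns marrow. Under inclusion 8 (5.1.2), if the "subject had anticancer treatment after biopsy, the bone marrow biopsy and aspiration should be repeated".

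**Ban during Screening (5.5.2).** "Subjects are prohibited from receiving the following therapies during the Screening and Treatment phase of this trial"; the list that follows includes antineoplastic systemic chemotherapy, biological therapy, immunotherapy and radiation.

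**The concern.** The baseline window is longer than the washout for part of the prior therapy. A subject can be scanned, receive more of the previous regimen, and then start trial drug. Every later scan is compared with a tumor measured before that last exposure. Shrinkage caused by the previous drug is then credited to pembrolizumab plus dinaciclib.

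ORR is the basis of the futility look (8.7) and the efficacy endpoint with a stated precision (8.8). The cohorts are single-arm, so no comparator carries the same bias and cancels it. The confirmation requirements (two months for a CLL PR in 12.7, two consecutive assessments for MM in 12.8) do not remove it, because they refer to the same old baseline.

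**Working it through.** **1. Overlap = oldest allowed baseline minus shortest allowed washout**

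| Prior therapy | Washout | Baseline | Overlap |
|---|---|---|---|
| Anticancer therapy in general (exclusion 3) | 14 d | 28 d | 28 − 14 = 14 d |
| Ibrutinib or similar, CLL (exception) | 7 d | 28 d | 28 − 7 = 21 d |
| Anticancer monoclonal antibody (exclusion 6) | 28 d | 28 d | 0 d |
| Investigational agent (exclusion 1) | 28 d | 28 d | 0 d |

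**2. Is the baseline reset before first dose?** The flow chart (6.0) schedules no scan, SPEP, UPEP or FLC on Cycle 1 Day 1, so it is not. CBC with differential is drawn that day, in general before dosing (note a).

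**3. A sequence that the text allows.** Routine CT on Day −27, a further course on Day −16, consent on Day −14, first dose on Day 1. The course is neither an antibody nor investigational. If Screening begins at consent, no rule is broken.

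**4. Who is exposed.** CLL needs one prior therapy, not failure of the last drug (inclusion 11). DLBCL subjects may enter after stopping a drug for toxicity before progression (inclusion 17). MM subjects must have progressed during or within 60 days of completing their last line (inclusion 14), so carried-over shrinkage is less plausible there.

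**5. Effect on the PR threshold.** Let the tumor sum of products fall by a fraction s between the old scan and first dose, and assume that the fall persists. The on-study fall needed to reach 50% against the old scan is 1 − 0.50/(1 − s).
- s = 20%: 1 − 0.50/0.80 = 37.5%
- s = 40%: 1 − 0.50/0.60 = 16.7%

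The values of s are assumptions.

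**6. The plan's own figures reproduce.** The exact one-sided 90% upper limit is 17.46% for 0/12 (plan: 17%) and 38.55% for 2/12 (plan: 39%). The largest exact 95% half-width at n = 30 is 18.7% (plan: 19%).

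**7. One misattributed response.**
- At n = 30 it adds 1/30 = 3.3 points. For example, 5/30 = 16.7% (5.6 to 34.7) becomes 6/30 = 20.0% (7.7 to 38.6).
- At the interim look, 0/12 becomes 1/12. The MM/DLBCL boundary is missed, and the 90% upper limit rises from 17.5% to 28.7%.

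**8. Illustration only.** Let m be the share of true non-responders scored as responders through carry-over. Observed ORR = p + (1 − p)m.

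| Rule | True p | m = 0 | m = 2% | m = 5% |
|---|---|---|---|---|
| P(0/12), MM/DLBCL | 5% | 0.540 | 0.424 | 0.292 |
| P(≤2/12), CLL | 20% | 0.558 | 0.502 | 0.422 |

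Neither m nor p comes from the documents.

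**The case against.** **Section 5.5.2 may already close the gap.** The flow chart labels Screening as Day −28 to −1. On that reading the Day −16 course above is prohibited. Exclusion 3 is also an eligibility floor and does not by itself permit treatment. This stands in part: a baseline taken after consent is protected from the listed therapies, so the exposure lies mainly in reused routine results. It does not settle the matter, because a scan and a later course can both precede consent. Read over the full 28 days, the ban also sits badly with the ibrutinib exception, which does permit treatment, and 5.5.2 itself limits thoracic radiation only within 14 days of first dose.

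**A carried-over response is hard to achieve.** The first CLL/DLBCL assessment is at Cycle 4 Day 1, nominally 3 × 21 = 63 days after first dose. In the example, shrinkage must still be visible 16 + 63 = 79 days after the last prior course, and CLL and MM also need confirmation. This stands and lowers the likely frequency. It does not exclude partial carry-over that lowers the on-study shrinkage needed (step 5).

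**The biopsy rule has another purpose.** It protects material for biomarker analysis. This stands: the rule is a useful model, and its absence for scans is not an internal contradiction.

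**Stronger readings that a reader might infer, and that the documents do not support:**
- *All prior therapy is affected.* Antibodies and investigational agents have no overlap.
- *The old baseline also produces false progression.* Regrowth after stopping an active drug would be scored even against a baseline taken the day after the last dose, so the mismatch is not its main cause and the fix largely would not cure it. Lymphoma progression is judged from nadir (12.9).
- *CLL blood counts share the problem.* A Cycle 1 Day 1 CBC exists. What is missing is a statement that it is the baseline.
- *The futility rules are materially compromised.* That rests wholly on assumed rates, and 8.7 leaves the decision to judgment.

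**Conclusion.** The gap is in the text, within limits. For prior therapy other than antibodies and investigational agents, a reused routine or pre-consent baseline can precede up to 14 days of further treatment, or 21 days for ibrutinib or similar in CLL. Any resulting shrinkage counts toward PR.

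The overlap in days and the 3.3 points per misattributed response follow from the documents. How often such a response occurs does not, and the 2% and 5% rates only illustrate sensitivity.

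Priority is modest. The primary objective is safety (3.1), and ORR is a secondary objective (3.2), although 8.4.1 lists it as the primary efficacy endpoint. MM and CLL are closed to enrollment (1.0), MM for lack of efficacy, so a new baseline rule can act only on DLBCL subjects still to be enrolled. For everyone else the issue is how the reported ORR is interpreted. This is a cheap improvement.

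**What to change.** 1. **Baseline rule (7.1.2.8).** State that the scan or M-protein/FLC used as the response baseline must be obtained after the last dose of prior anticancer therapy, and that a routine pre-consent result is acceptable only if no anticancer therapy followed it. The overlap then becomes 0 days in every class. State also that the predose Cycle 1 Day 1 CBC is the baseline for CLL counts.
2. **Subjects already enrolled, including the closed cohorts.** Prior cancer treatments are recorded in the trial database (7.1.1.5.3). In the supplemental SAP (8.0, 8.6.6), list subjects whose baseline preceded their last prior therapy, as far as the recorded dates allow. Add an ORR sensitivity analysis that counts responders among them as non-responders.
3. **Reconcile** exclusion 3, including the ibrutinib exception, with the Screening-phase ban in 5.5.2, and say when Screening begins for that purpose. No washout length is proposed here.

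**Cost.** A few sentences of protocol text, one listing and one sensitivity table. The screening scan is already scheduled. The downside is that a few subjects could not reuse an older routine scan. Residual drug effect after the last prior dose would remain.

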5.2 Trial Treatment(s)

The treatments to be used in this trial are outlined below in [Table 2](#).

Table 2 Trial Treatments

Drug	Dose/ Potency	Dose Frequency	Route of Administration	Treatment Period	Use
Pembrolizumab (MK-3475)	200 mg	Every 21 days	IV infusion	Until PD, or up to a maximum of 35 cycles (approximately 2 years)	Investigational
Dinaciclib (MK-7965)	14 mg/m ² (Cycle 1 dosing per Table 3)	Table 3	IV infusion	Until PD, or up to a maximum of 35 cycles (approximately 2 years)	Investigational

Abbreviations: IV = intravenous; PD = progressive disease.

Subjects will receive pembrolizumab and dinaciclib as described in [Table 3](#). In Cycle 1, pembrolizumab 200 mg IV (30-minute infusion) will be administered on Day 1; dinaciclib 7 mg/m² IV (2-hour infusion) will be administered on Day 1, and 10 mg/m² IV on Day 8. Each cycle is 21 days. In Cycle 2 and beyond, pembrolizumab will be administered on Day 1, and dinaciclib 14 mg/m² will be administered on Day 1 and Day 8.

Table 3 Dosing Schedule of Pembrolizumab and Dinaciclib

Cycle	Day	Pembrolizumab	Dinaciclib
Cycle 1	1	200 mg	7 mg/m ²
	8	-	10 mg/m ²
	15	-	-
Cycle 2+	1	200 mg	14 mg/m ²
	8	-	14 mg/m ²
	15	-	-

If there are ≥ 5 subjects with DLTs within the initial cohort of 12 subjects in Dose Evaluation, dinaciclib dosing will be evaluated according to Section 5.2.1.3.4 and [Table 13](#).

Trial treatment should begin on the day of treatment allocation or as close as possible to the date on which the subject is allocated/assigned. Treatment allocation by non-random assignment will be done using an IVRS/IWRS.

Dinaciclib and pembrolizumab will be provided centrally by the Sponsor or locally by the trial site, subsidiary or designee, depending on local country operational or regulatory requirements.

The investigator shall take responsibility for and shall take all steps to maintain appropriate records and ensure appropriate supply, storage, handling, distribution and usage of trial treatments in accordance with the protocol and any applicable laws and regulations.

